Official Title:	Hypnosis for Chronic Pain Relief in Cancer Survivors
NCT number:	03867760
Document Type:	Study Protocol and Statistical Analysis Plan
Date of the Document:	January 28, 2019

RESEARCH PROTOCOL

Methods and Design

Design. The study design is a two-arm RCT. The study uses an expanded protocol from the pilot RCT. The primary outcome (pain intensity) and secondary outcomes (pain interference, anxiety, depression, fatigue, and sleep disturbance) will be assessed at baseline, mid-study, and end of study. In addition, pain intensity and anxiety will be assessed daily. Participants will be randomly assigned to the RHI or an attention control condition (relaxation recording). Furthermore, an extreme phenotype approach will be taken to study brain states as a mechanism for hypnosis-induced pain reduction. Five participants from each group who score low (score = 0 - 1)¹ on the hypnotic suggestibility scale and 5 participants from each group who score high (score = 4 - 5)¹ will be invited to undergo qEEG measurement.

Sample and Settings. A convenience sample of 100 cancer survivors with chronic pain will be recruited from the Seattle Cancer Care Alliance (SCCA) Survivorship Clinic. SCCA is a National Cancer Institute-designated comprehensive cancer center where more than 6,000 patients with cancer received treatment last year. In 2016, 194 patients were seen at the Survivorship Clinic (based on chronic pain prevalence estimate of 39%, 76 patients with pain).

Power Analysis. Table 1 shows the minimal detectable change in the mean of the RHI group that can be detected given a total sample of 100 participants and 80% power, based on standard deviations observed in our prior research.

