Participant Inclusion and Exclusion Criteria. Participant inclusion criteria are: (1) self-reporting moderate or higher pain on average during the last week (> 3 on a 0-10 pain intensity numeric scale), (2) self-reporting chronic pain related to cancer or its treatment, (3) completed active cancer treatment other than maintenance therapy, (4) being \geq 18 years of age, (5) functional fluency in English, and (6) mentally and physically able to participate and complete surveys. Participant exclusion criteria are: (1) a history of seizure disorder and (2) a significant brain injury or skull defect. Both exclusion criterion may impact qEEG measurement. We will not exclude potential participants based on use of pain medication, rather we will collect this information (drug, dose) and control for it in the data analysis.

Participant Recruitment. Staff at the SCCA Survivorship Clinic will screen Survivor Surveys completed by patients prior to their initial clinic visit from the past 2 years and during the study to identify patients who meet the pain intensity inclusion criteria. Names and contact information for patients will be given to the research team who will mail an information letter describing the study. The letter will include an opt-out postcard to be returned if the patient is not interested in being contacted by telephone about the study. Two weeks after the letters are mailed, patients will be contacted by telephone to further screen for eligibility and describe the study. If the patient is eligible and interested in participating, verbal and written consent to participate will be obtained. A study visit will be scheduled at the UW Health Sciences Center (HSC) for completion of the Stanford Hypnotic Clinical Scale and assignment of the intervention. The consent form and baseline questionnaires will be mailed to the participant to sign and complete respectively and return at the Week 0 (baseline) study visit.

Group Assignment. A SPSS randomization program will yield group assignments which will be placed in opaque, sequentially numbered sealed envelopes. Once the participant returns the completed baseline questionnaires and completes the in-person hypnotic clinical measure at the Week 0 study visit, the appropriate envelope will be opened and the participant will be notified of his/her group assignment. Based on their high or low hypnotic suggestibility score, eligible participants will be invited to participate in the qEEG study arm.

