questionnaires (\$25) and diary (\$25). Participants also will be given \$25 to pay for parking and gas, or for public transportation for the visit to the UW HSC. The 20 participants undergoing qEEG will receive an additional \$50 after completing each qEEG for a total of \$150. They also will be given \$25 to pay for parking and gas, or for public transportation to the UW IBIC for two visits (\$50). Data will be managed using REDCap (Research Electronic Data Capture).⁹ The RA will be responsible for data entry and I will verify its accuracy.

Data Analysis. *Aim 1: Does the RHI work? Evaluate the efficacy of RHI in reducing self-reported pain intensity (primary outcome) and pain interference, anxiety, depression, fatigue, and sleep disturbance (secondary outcomes) at 4 weeks compared to the attention control condition (relaxation recording).* We will use ANCOVA controlling for baseline scores and co-variates including pharmacologic treatments to test whether *mean pain intensity* at week 4 differs between the RHI and relaxation groups. The same analysis will be done for the secondary outcomes. In addition, we will graphically describe trajectories of daily pain and anxiety at Weeks 0, 2, and 4, based on the Daily Diary for pain intensity and anxiety in the RHI and relaxation groups. This approach will allow us to understand whether an increased dose of the intervention (i.e., 4 weeks vs. 2) is necessary to achieve significant reduction in pain intensity.

Aim 2: For whom does the RHI work? Examine if psychological factors (hypnotic suggestibility, mental absorption, treatment outcome expectancy) moderate the relationship between RHI and pain intensity at weeks 0, 2, and 4. The following multiple regression model will be estimated:

$\text{PAIN}_{\text{week}2} = \text{Pain}_{\text{week}0} + \text{PSY}_{\text{week}0} + \text{RHI} + \text{PSY}_{\text{week}0} \times \text{RHI}$, where moderator effects will be indicated by the interaction term $\text{PSY}_{\text{week}0} \times \text{RHI}$. We will measure Cohen's d for each of the levels of the moderator and compare them to determine the moderator effect. The resulting effect size will be used to estimate the sample size in a larger follow-up study (e.g., R01).

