Aim 3: How does the RHI work? Compare brain states as measured by qEEG in cancer survivors with chronic pain receiving the RHI relative to the attention control condition (relaxation recording) at weeks 0, 2, and 4. We will use multiple regression models controlling for baseline scores and co-variates (e.g., medication use) to compare the change in theta activity from *pre-session* to *during session* between RHI and relaxation groups. We will also compare the change in theta activity from *pre-session* to *post-session* between groups. This will be replicated for all 3 time points: Weeks 0, 2, and 4. Replication allows us to assess if theta activity

changes during the study period. We will also explore other bandwidths (e.g., alpha, beta, delta, gamma) in our analysis. Medium or larger effect sizes for changes in bandwidth activity will be used to indicate that more formal testing in future research is warranted. *Explore the mediation effects of brain states (theta activity) on pain intensity at weeks 0, 2, and 4.* Cross-sectional analyses will examine mediation at weeks 0, 2, and 4 for how RHI and theta activity jointly affect pain intensity. The mediating effects model implicit in **Figure 1** will be tested using multiple regression models. Effect sizes (Cohen's d) will be computed for looking at the biological mechanism in a larger, more definitive study. *Structured interviews.* Transcribed interview data will be organized in ATLAS.ti7 (Scientific Software Development, Berlin, Germany). Content analysis^{10,11} will be used to understand the barriers and facilitators associated with undergoing qEEG measurement and perceptions on how the intervention works to reduce pain.

In summary, this study is extremely important because it will provide scientific evidence on the efficacy of a symptom self-management intervention that cancer survivors can easily use to manage a distressing symptom. Furthermore, this study is innovative in that it will increase our understanding of how this intervention works and who will most likely experience pain reduction when using this low-cost, accessible, and convenient intervention.

References

1. Morgan AH & Hilgard JR. (1978). The Stanford Hypnotic Clinical Scale for adults. *The American Journal of Clinical Hypnosis*, 21, 134-47.
2. [name] M. (2011). *Hypnosis for chronic pain management: therapist guide*. Oxford University Press.

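### The Aim 3 theta model leaves out the high/low suggestibility factor on which the 20 qEEG participants are selected; adding it is a cheap, minor improvement.

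*Combined protocol and SAP*

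**What the plan says.** The Design paragraph states that "an extreme phenotype approach will be taken to study brain states as a mechanism for hypnosis-induced pain reduction". It takes "Five participants from each group who score low (score = 0 - 1") and five per group who score 4 to 5. The Group Assignment paragraph confirms the selection: "Based on their high or low hypnotic suggestibility score, eligible participants will be invited to participate in the qEEG study arm".

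Under Data Analysis, Aim 3, theta is analysed with "multiple regression models controlling for baseline scores and co-variates (e.g., medication use) to compare the change in theta activity from" pre-session to during the session, and then from pre-session to post-session, between the RHI and relaxation groups, at each of Weeks 0, 2 and 4. The result feeds a go-forward signal: "Medium or larger effect sizes for changes in bandwidth activity will be used to indicate that more formal testing in future research is warranted". No value for medium is given, and the SD that scales the effect size is not stated.

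Suggestibility appears as a model term only in Aim 2, where pain intensity is the outcome. There the plan does report by level: "We will measure Cohen's d for each of the levels of the moderator and compare them to determine the moderator effect".

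**The concern.** The factor that decides who enters the qEEG sub-study is absent from the written analysis of its main measure. Two things follow.

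First, sampling the two ends of the scale makes a high/low difference in mean theta change more likely to matter. If such a difference exists and the model has no term for it, it is counted as noise. The arm difference in raw units is unaffected, but a standardised effect size divides by an inflated SD and comes out smaller. The plan's signal is a threshold on that standardised quantity.

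Second, sampling five low and five high scorers per arm allows theta to be shown separately for each, and the plan does not ask for this. The covariate list is open, so suggestibility could be added as a covariate, but that alone would give neither an interaction nor an estimate by suggestibility group.

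**Working it through.** **Inputs from the documents.** Five low and five high scorers per arm (Design); 20 qEEG participants (payment paragraph); an arm comparison adjusted for baseline and covariates (Aim 3); two-sided alpha 0.05 (Table 1; no separate value is given for qEEG).

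**Assumptions.** Medium means |d| ≥ 0.5. One contrast is examined. Within-stratum SD is 1. No covariates are included. D is the high-minus-low difference in mean theta change, in within-stratum SDs. The documents give no value for D, so 0, 1 and 2 are shown.

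**1. The plan's own figure.** 2 arms × 2 strata × 5 = 20, as stated.

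**2. Bias.** Each arm is half high and half low, so D adds D/2 to both arm means and cancels in the difference. There is no bias in the selected sample.

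**3. Inflation of the SD.** Without the term, each arm's sum of squares gains (5×5/10)D² = 2.5D². Over two arms and 18 df, the expected pooled variance is 1 + 5D²/18.
- D = 1: variance 1.278, SD 1.130, so a true 0.8 becomes 0.8/1.130 = 0.71.
- D = 2: variance 2.111, SD 1.453, so 0.8/1.453 = 0.55.

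The sample d has a small upward bias. In simulation (400,000 runs) its mean is about 0.74 and 0.57 in these two cases, against 0.84 at D = 0.

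**4. Signal rate.** The cut-off in t units is 0.5/√(2/10) = 1.118. For a uniform 0.8 SD effect the noncentrality is 0.8/√0.2 = 1.789; at D = 0 (df 18) the signal fires 75% of the time. The other rates below come from the simulation.

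| High/low difference D | Signal rate without the term | With term and within-stratum SD |
|---|---|---|
| 0 | 75% | 75% |
| 1 | 70% | 75% |
| 2 | 57% | 75% |

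**5. The same calculation with no effect.** With the term, or at D = 0, the signal fires about 28% of the time (two-sided, t = 1.118). Without the term the simulation gives about 22% at D = 1 and 12% at D = 2. The term therefore restores the intended scale of d; it does not lower the false-signal rate.

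**6. Why the signal must not move to the subgroups.** For 5 v 5 the SE is √(2/5) = 0.632 and the cut-off is 0.5/0.632 = 0.791. With no effect and pooled error (df 16), each stratum reaches |d| ≥ 0.5 44% of the time, and at least one of the two does so 68% of the time.

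**7. Precision, 95% CI half-widths in SD.**
- Overall: 2.101 × √0.2 = 0.94 (df 18); 2.120 × √0.2 = 0.95 (df 16).
- Within a stratum: 2.120 × √(2/5) = 1.34.
- Interaction: 2.120 × √(4/5) = 1.90.

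Interaction power (noncentral t, df 16) is 13%, 18% and 35% at 0.8, 1.0 and 1.5 SD; 80% power needs about 2.67 SD.

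**The case against.** The strongest reply is that nothing here is an error. Aim 3 sets out to compare RHI with relaxation, and the planned model does that without bias. No high/low comparison of theta is a stated objective, and the question of for whom the intervention works belongs to Aim 2. With five per cell, any stratified result will be very imprecise. All of this stands, and it is why the point is a minor improvement.

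A reader might infer more: that a theta effect confined to high scorers is being halved, so that 0.8, 1.0 or 1.5 SD averages to 0.4, 0.5 or 0.75 SD. The arithmetic is right, but it requires no effect in low scorers, and the documents say nothing of the kind. If the effect is similar in both strata, pooling is the better estimate. Under that same assumption the high estimate would exceed the low one 81%, 87% or 95% of the time, but chance alone gives 50%.

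A reader might also infer that suggestibility is missing from the mediation model. That model is defined through Figure 1, which is not visible, so no claim is made about it.

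Finally, stratified reporting can mislead. With a uniform 0.8 SD effect, one stratum reaches d ≥ 0.5 and the other does not about 43% of the time. The fix has to guard against reading that as a responder pattern.

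**Conclusion.** The point holds as a minor, inexpensive improvement to the written theta analysis. The arm contrast is valid as planned. The avoidable loss is that a high/low difference in theta change would deflate the effect size behind the signal: for a uniform 0.8 SD effect, from about 75% to 70% or 57% when the strata differ by 1 or 2 SD, and not at all if they do not differ. The chance of a signal under no effect falls as well, so the gain is a correctly scaled d, not a better error rate at a fixed cut-off.

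These figures assume 0.5 as medium, d computed from the pooled within-arm SD, one contrast and no covariates. The planned baseline term may already absorb part of any high/low difference, which would reduce the gain. The extreme-phenotype sampling also goes unused for theta. The signal only prompts further research, and the primary pain analysis is not affected.

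**What to change.** 1. Add the high/low suggestibility group to the Aim 3 theta models, with RHI × group included for estimation and not for testing. Code the factors so that the RHI coefficient is the average over the two strata. Compute the overall d from the within-stratum residual SD.
2. Report the RHI-minus-relaxation theta contrast with a 95% CI overall and, descriptively, in high and low scorers. This extends to theta the by-level reporting that Aim 2 already plans for pain. If the ordering of the two estimates is discussed, state that chance alone puts high above low half the time.
3. State that the medium-or-larger signal applies to the overall contrast only, never to the 5 v 5 estimates (68% against 28% with no effect).

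**Cost.** SAP wording only; the score and the recordings are collected anyway. Residual df fall from 20 − 2 = 18 to 20 − 4 = 16, and to 20 − 6 = 14 after one baseline and one medication term. The overall half-width goes from 0.94 to 0.95 SD before those covariates. The by-stratum and interaction intervals are wide (about ±1.34 and ±1.90 SD), and interaction power is 13% to 35% for 0.8 to 1.5 SD, so these results can be described but not used to decide anything.

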Intervention/Independent Variables. *Hypnosis Intervention.* The RHI consists of four 12- 18-minute digital recordings that I will make using standardized hypnosis scripts for pain reduction² and upload to a MP3 player. The scripts were developed for patients with chronic pain and tested by a psychologist who is an expert in hypnosis research ([name], co-mentor). Participants will listen to the recordings daily for 28 days in the prescribed order (4 recordings for 3 days each, and then any recording for the remaining 16 days). Selected recordings will be noted by the participant on the Daily Diary. The script includes an induction, suggestions for how to access inner resources and manage pain, and post-hypnotic suggestions for permanence of hypnosis

Table 1. Minimal Detectable Change in RHI Group

For N=100 (50/group), 80% power, alpha = 0.05, two-sided

Pain Score Standard Deviation		
Small SD (1.0)	Expected SD (1.5)	Large SD (2.0)
-0.57	-0.85	-1.13

benefits and self-hypnosis practice. Attention Control. The relaxation recordings will be uploaded to a MP3 player. Four different 12- 18-minute recordings of the selected genre will be listened to daily for 28 days (same prescribed order as the RHI).

Table 2a. Instruments.

Aim	Study Measures	Variable Measured	Week 0	Daily	Week 2	Week 4
1	*PROMIS 29 v. 1.0 29-item questionnaire, Cronbach's α 0.92-0.97. ³	Pain interference, anxiety, depression, fatigue, sleep	X		X	X
1	*PROMIS v.1.0-Pain Intensity 3a 3-item questionnaire, Cronbach's α 0.92-0.97. ³	Pain intensity	X		X	X
2	*PROMIS Self-Efficacy for Managing Symptoms	Self-Efficacy	X			X
3	qEEG	Brain activity/state	X		X	X

* National Institute of Nursing Research (NINR) Common Data Elements

Table 2b. Instruments.

Aim	Study Measures	Variable Measured	Week 0	Daily	Week 2	Week 4
1	Daily Diary 9-item questionnaire completed at bedtime, feasibility of participants completing it on a daily basis was established in pilot study.	Pain intensity, anxiety, and use of RHI or relaxation recording (including which recording used)		X		
2	Stanford Hypnotic Clinical Scale for Adults 5-item scale, 20 minutes to administer, product-moment correlation between total score and Stanford Hypnotic Scale C total score 0.72. ¹	Hypnotic suggestibility	X			
2	Tellegen Absorption Scale 34-item multi-dimensional scale, ⁴ test-retest reliability 0.85. ⁵	Absorption (Imaginative involvement, tendency to become mentally absorbed)	X			

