qEEG Protocol: The participant will complete a 0-10 pain intensity numeric scale pre- and post-qEEG. During the qEEG, the intervention group participant will listen to the RHI and the attention control group participant will listen to the relaxation recording via the MP3 player (Table 3). The EEG technologist will fit an electrode cap with premeasured sites using the international 10/20 system⁷ to the participant's head and the participant's scalp and will prep the earlobes with Nuprep (Weaver and Company, Aurora, CO, USA). The electrode sites will be filled with Electro-Gel (Electro-Cap International, Eaton, OH, USA) and prepped to ensure impedance values between 3 and 5 Kohms between each electrode site and each ear individually. The signals will be amplified using a bandpass of 0.53-70 Hz and sampled at the rate of 250 Hz. for 10 minutes (eyes closed) with an EGI Geodesic EEG System 300 using 128-channel HydroCel Nets. Participants will be monitored throughout the recording to ensure that they remain awake.

Per the UW IBC, raw recordings will be band-pass filtered between 0.5-100 Hz, and exported to Matlab (MathWorks, Natick, MA, USA) and then remontaged to the average reference montage. Plotted data will be inspected for potential artifacts (e.g., evidence of eye blinks, eye movements, body movements) and entire epochs will be removed if one or more channels exhibit presence of artifact. qEEG spectrum will be calculated from the first 2 minutes of artifact-free data with fast Fourier transform using 4-second epochs with 1/32 seconds of overlapping window advancement factor. The relative EEG power will be computed for each of five bandwidths (delta, 1.5-4 Hz; theta, 4-8 Hz; alpha, 8-13 Hz; beta, 13-30 Hz; gamma, 30-55 Hz), and the power estimates will be used for all subsequent analyses by our research team. Relative power measures show a closer correspondence to underlying cortical activity than does absolute power.⁸

All participants will receive \$50 for their participation, which will be distributed as follows: after return of the baseline

Table 3. qEEG Measurement Timeline

	Pre-Session	During Session	Post-Session
Week 0	10 minutes eyes closed	13 minutes RHI or relaxation	10 minutes eyes closed
Week 2	10 minutes eyes closed	13 minutes RHI or relaxation	10 minutes eyes closed
Week 4	10 minutes eyes closed	13 minutes RHI or relaxation	10 minutes eyes closed

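### Aim 3's theta contrasts measure the acute response at each visit; a lasting between-arm shift in resting theta cancels out of them, and no cross-visit comparison is planned

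*Combined protocol and SAP*

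**What the plan says.** Data Analysis, Aim 3, specifies two between-arm comparisons of theta. The first is to "compare the change in theta activity from *pre-session* to *during session* between RHI and relaxation groups". The second reads: "We will also compare the change in theta activity from *pre-session* to *post-session* between groups". Both use the pre-session recording of the same visit as the reference. The plan continues: "This will be replicated for all 3 time points: Weeks 0, 2, and 4. Replication allows us to assess if theta activity" changes over the study period. It writes no contrast between visits, no group-by-visit term, and no comparison of Week 2 or Week 4 pre-session theta with Week 0.

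The adjustment is described as follows: "We will use multiple regression models controlling for baseline scores and co-variates (e.g., medication use"). The term baseline scores is not defined for the EEG models. A further cross-sectional mediation analysis uses theta activity at each of the three weeks without saying which recording, or whether a level or a change is meant.

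Table 3 schedules a 10-minute eyes-closed recording before each session at Weeks 0, 2 and 4. According to the Week 0 Study Visit text, the first EEG coincides with the start of the intervention, and the later ones fall within a day of the study measures taken after 14 and 28 days of use.

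**The concern.** The pre-session recording precedes any use of the intervention only at Week 0. At Weeks 2 and 4 it follows about two and four weeks of daily listening, and the RHI scripts include "post-hypnotic suggestions for permanence of hypnosis" benefits. The script is therefore meant to act beyond the session, and resting theta at the later visits may already differ between arms. If it does, the reference for the within-visit change moves with treatment.

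At stake is a stated purpose of the aim. Aim 3 uses medium or larger effect sizes to decide whether formal testing in later research is warranted. An effect of RHI that shows mainly as a sustained shift in resting theta would produce a small or null within-visit contrast, and could be passed over for a reason unrelated to its size.

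**Working it through.** **Inputs from the documents.** Two within-visit contrasts at three visits (Aim 3); a pre-session recording at every visit (Table 3); 20 EEG participants, which is 10 per arm, 5 of low and 5 of high suggestibility (Design). The documents give no mean, SD, correlation or target effect for theta.

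**Assumptions.** Theta SD is set to 1, and effects are additive. L is the lasting between-arm shift in theta shared by all recordings at a later visit. S is the extra between-arm response in session. ρ is the correlation between any two recordings of one participant, varied over 0.5, 0.7 and 0.9.

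**Step 1: the planned contrast.** At Week 2 or Week 4 the between-arm differences are:

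- pre-session: L
- during session: L + S
- change: (L + S) − L = S

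L cancels. The same holds for pre- to post-session, with S as the extra post-session response.

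**Step 2: check by least squares** on 200,000 simulated participants. Ranges run over the three values of ρ.

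| Assumed effects | Change, unadjusted or adjusted for Week 0 theta | Pre-session theta adjusted for Week 0 pre-session theta |
|---|---|---|
| L = 0.8, S = 0 | 0.00 | 0.80 |
| L = 0.8, S = 0.5 | 0.50 | 0.79 to 0.80 |
| L = 0, S = 0.5 | 0.50 | 0.00 |

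The second and third rows give the same planned estimate, although only one of them contains a lasting effect. Adjusting the change for Week 0 theta does not separate them. The proposed comparison does.

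**Step 3: if baseline scores meant the same-visit pre-session value.** The adjusted contrast would then estimate S + L(1 − ρ).

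- With L = 0.8 and S = 0: 0.8 × 0.5 = 0.40, 0.8 × 0.3 = 0.24 and 0.8 × 0.1 = 0.08 for ρ = 0.5, 0.7 and 0.9.
- With S = 0.5, adding 0.5 to each gives 0.90, 0.74 and 0.58.

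Part of L gets through, but mixed with S, so the estimate describes neither.

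**Step 4: the mediation analysis.** If theta there is a within-visit change, its RHI-to-theta path loses L as in Step 1. If it is the pre-session level, the path carries L. If it is the during-session level, the path carries L + S (0.8 + 0.5 = 1.3 in the second row of the table). The text does not say which applies.

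**Step 5: precision of the added comparison.** The only power figures in the plan are those of Table 1, for pain with 50 per group. A two-sample t calculation (noncentral t, 98 df) gives 0.566, 0.849 and 1.132 against the stated 0.57, 0.85 and 1.13, so the method reproduces them. The same calculation with 10 per arm (18 df) gives 80% power only at d of about 1.32. Power is about 18% at d = 0.5 and 39% at d = 0.8. Without covariates, the 95% half-width is 2.101 × √(1/10 + 1/10) = 0.94 SD. Adjusting for Week 0 theta (17 df) multiplies the SD by √(1 − ρ²). The half-width is then 2.110 × 0.447 × √(1 − ρ²), which is about 0.82, 0.67 and 0.41 SD for ρ = 0.5, 0.7 and 0.9. Further covariates cost more degrees of freedom.

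**The case against.** The acute response to a session is a legitimate target for a study of mechanism, and the sentence about replication directly follows the within-visit contrasts. It can fairly be read as asking whether that response changes over the study, which three repetitions do show descriptively. This stands: a reader might infer that the plan can say nothing about change in theta, and that is too strong. What it lacks is the resting component.

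Theta contrasts are not the only use of theta. Aim 3 opens with a general comparison of brain states between arms at all three weeks, and the mediation analysis might use levels. Figure 1, which may define the mediator, is not shown in the available text. This also stands, so the gap cannot be called complete; but nothing written names the resting comparison.

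Baseline most naturally means Week 0. The recruitment text labels the Week 0 visit that way, and the Aim 2 model adjusts for Week 0 pain. The text therefore does not support a claim that the plan adjusts for a variable already affected by treatment. Step 3 shows only why one confirming phrase is worthwhile.

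A reader might also infer that a lasting effect would look like a fading one. That needs in-session theta to stay level while resting theta rises, a ceiling the documents do not describe. If both rise together, the contrast is unchanged: it is blind to the shift, not reversed. Nor do the documents say that resting theta is the brain state that matters most for pain at four weeks. The permanence suggestions concern the benefits of hypnosis, not resting EEG.

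Finally, the aim is exploratory, has 10 per arm, and leaves the primary outcome untouched. That limits the weight of the point, but an aim built on effect sizes still needs the effect size that answers its stated question.

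**Conclusion.** The point holds in a limited form. The two specified theta contrasts isolate the acute response and remove any between-arm shift common to all recordings at a visit. They therefore support only part of the stated purpose of the replication. The removal is exact for change scores under the additive model, whether unadjusted or adjusted for Week 0 theta. It would be partial, and confounded with the acute response, under same-visit adjustment. How much is lost in practice is unknown: the values of L, S and ρ are assumptions, and the documents do not establish that a lasting shift exists. The gap is in the analysis and not in data collection. The plan should be amended, but neither the primary outcome nor Aim 1 is affected.

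**What to change.** Add to Aim 3 a between-arm comparison of pre-session theta at Week 2 and another at Week 4, each adjusted for Week 0 pre-session theta, reported as an effect size with a confidence interval and labelled exploratory. Name this as the analysis of change in resting theta over the study, and describe the within-visit contrasts as measures of acute response. Confirm that baseline scores in the EEG models means the Week 0 pre-session value. State which recording supplies theta in the mediation models, and whether it enters as a level or a change.

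The cost is some wording and two regressions on recordings already scheduled, with no new visit or procedure. The downside is two more exploratory estimates of low precision, which should be read from their intervals and not from significance.

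### Aim 3's three separate weekly regressions give no standard error or interval for a change in the theta effect between visits, which the repetition is meant to assess

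*Combined protocol and SAP*

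**What the plan says.** The Aim 3 paragraph of the Data Analysis section sets out the model: "We will use multiple regression models controlling for baseline scores and co-variates (e.g., medication use) to compare the change in theta activity" between groups, once from pre-session to during session and once from pre-session to post-session. It continues: "This will be replicated for all 3 time points: Weeks 0, 2, and 4". The purpose follows directly: "Replication allows us to assess if theta activity" varies over the course of the study. The mediation analysis is also done one week at a time: "Cross-sectional analyses will examine mediation at weeks 0, 2, and 4".

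The sample comes from the Design paragraph: "Five participants from each group who score low" on the suggestibility scale and "5 participants from each group who score high". That makes 10 per group and 20 in all, which agrees with the payment paragraph ("The 20 participants undergoing qEEG will receive an additional" sum per session). Every participant is due at all three visits.

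Aim 3 is judged by effect size: "Medium or larger effect sizes for changes in bandwidth activity will be used to indicate that more formal testing in future research is warranted". The documents mention no repeated-measures model, within-person correlation, arm-by-week term or method for missed qEEG visits.

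**The concern.** Whether theta changes during the study is a question about a difference between visits in the same people. The plain reading of the plan is one regression per visit for each phase contrast. Each regression estimates the group effect at its own visit, and none estimates the difference between two visits. One could subtract one weekly estimate from another. But separate fits carry no covariance between weeks, so the subtraction has no valid SE or interval.

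Two things are at stake. First, a reader left to compare three weekly results by eye will tend to treat them as independent, and so judge the change against too large an error. Second, someone who misses one session contributes nothing to that week's fit, although their other sessions carry information about it. With 10 per group, neither loss is welcome, and the 20 × 3 = 60 sessions needed to avoid both are already planned.

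**Working it through.** **Inputs.** Ten per group and three visits (Design; Aim 3). The documents give no theta SD, between-visit correlation (ρ) or qEEG dropout rate. Results are therefore in units of the single-visit SD of the theta change, with ρ assumed from 0.3 to 0.9.

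**The plan's own figure.** The only power figure is Table 1, for pain intensity at 50 per group. A two-sample t calculation gives detectable differences of 0.566, 0.849 and 1.132 against the stated 0.57, 0.85 and 1.13, so it reproduces. It does not concern theta, and Aim 3 has no figure of its own to check.

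**Step 1: SE of the group effect at one visit.** √(1/10 + 1/10) = √0.20 = 0.447.

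**Step 2: SE of the change in group effect, Week 4 minus Week 0.** The variance is 0.20 + 0.20 − 2ρ(0.20) = 0.40(1 − ρ). Treating visits as independent sets ρ = 0 and gives √0.40 = 0.632. The half-width is 2.101 × SE, where 2.101 is the t value on 20 − 2 = 18 df.

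| Assumed ρ | Paired SE | SE if treated as independent | Ratio, independent to paired | 95% half-width, paired |
|---|---|---|---|---|
| 0.3 | √0.28 = 0.53 | 0.63 | 1.20 | 1.11 |
| 0.5 | √0.20 = 0.45 | 0.63 | 1.41 | 0.94 |
| 0.7 | √0.12 = 0.35 | 0.63 | 1.83 | 0.73 |
| 0.9 | √0.04 = 0.20 | 0.63 | 3.16 | 0.42 |

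This assumes complete data, equal SDs across visits and groups, and no covariate adjustment. The independent half-width would be 2.101 × 0.632 = 1.33.

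**Step 3: do the weekly estimates lose precision?** A joint model with arm-by-week and covariate-by-week terms and an unstructured within-person covariance was compared with three separate regressions.

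- Complete data, same covariates each week: the SE ratio was 1.000 at every week for ρ from 0.3 to 0.9. In one worked example both approaches gave effects of 0.814, 0.203 and 0.657 with SEs of 0.472, 0.521 and 0.393.
- Complete data, covariate measured afresh each week (assumed correlation 0.6 between weeks): the joint SE was about 0.3% to 3% smaller.

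**Step 4: missed visits.** Assume 2 people missing at Week 2 and 4 at Week 4, with common covariates and known covariance. Over ρ from 0.3 to 0.9, the joint-model SE is unchanged at Week 0, 0.5% to 5% smaller at Week 2, and 1.4% to 10.5% smaller at Week 4.

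**The case against.** The strongest defence is that Aim 3 is exploratory. It claims no alpha or power, uses effect sizes only to decide whether later research is worthwhile, and states its aim as a comparison at each of three weeks. For those weekly comparisons, separate regressions are adequate. This stands, and it limits the severity. It does not cover the further statement that repetition will show change: an effect-size judgement on change still needs an estimate of that change and its uncertainty. The sentence might instead refer to theta levels within each group rather than the difference between groups. That reading also needs a within-person contrast between visits, which the plan lacks.

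Three stronger readings are tempting, and the documents support none of them.

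- A reader might infer that every Aim 3 estimate is less precise than the data allow. Step 3 shows otherwise for complete data with common covariates. Weekly gains need missed visits, week-varying covariates or extra variance assumptions, and were small to modest in the cases tried.
- A reader might infer that the main estimate should be the effect averaged over visits. Its SE relative to one visit is √((1 + 2ρ)/3), or 0.73, 0.82, 0.89 and 0.97 at ρ of 0.3, 0.5, 0.7 and 0.9. But the plan never targets that average, so the ratio compares two different quantities. Under Week 0 Study Visit, qEEG participants start the intervention at that visit, so the average would mix first exposure with two and four weeks of practice. It is a clean summary only if the effect is stable, which is the question being asked.
- A reader might infer that the plan claims independent replication. In context the word means repeated at each visit. No independence is asserted and no results are combined.

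**Conclusion.** The point holds in a limited form. The plan states a question about change in theta over the study, and its three unlinked regressions supply no estimate, SE or interval for change in the group effect. They also discard a person from any week missed, and no method for that is stated.

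Comparing weekly results as independent would overstate the SE of the Week 4 minus Week 0 contrast by a factor of 1.20 to 3.16 for ρ of 0.3 to 0.9. Those values rest on assumed correlations and equal variances. Even the correctly paired interval is wide unless ρ is high (half-width 0.94 SD at ρ = 0.5), so the gain is an honest answer to the stated question rather than a precise one. Severity is low: Aim 3 is exploratory, and the primary pain analysis is untouched.

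**What to change.** For each phase contrast (pre-to-during and pre-to-post), fit one linear mixed model to all three visits with:

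- arm, week and arm × week;
- Week 0 pre-session theta, the planned medication covariate and the high/low suggestibility stratum;
- a participant random intercept and small-sample degrees of freedom.

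State that the baseline score means Week 0 pre-session theta, which is recorded before the first listening. A later visit's pre-session theta is measured after randomisation and may itself be affected by practice.

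Report the weekly arm effects from this model, as planned. Report the arm × week contrasts (Week 2 minus Week 0, Week 4 minus Week 0) with 95% intervals as the answer on change. An effect averaged over visits may be shown as a supplementary summary, not as the main estimate. State that people with a missed visit stay in the model, on a missing-at-random assumption.

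The cost is analysis wording only, with no new data. The downside is that 20 people support only a simple covariance structure. A random intercept assumes equal variances and equal correlations across visits, and with shared covariate slopes the weekly estimates will not match separate fits exactly. A two-sample comparison of each person's Week 4 minus Week 0 difference is an easy check on the main contrast.
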